Al Azhar university
Faculty of medicine
Urology department

Retrograde Intrarenal Surgery for Renal Stones in Children: A prospective Analysis of Feasibility and Outcomes

Al-Azhar University
January 2023

INTRODUCTION:

The incidence of paediatric urolithiasis is on a rising trend globally,[1] and the treatment of stones in children poses a major challenge. Percutaneous nephrolithotomy (PCNL) and shock-wave lithotripsy (SWL) are the established forms of treatment for children with renal stones. despite its non-invasive and safe nature, coupled with high stone-free rates in children, necessity of multiple sessions under anesthesia and increased radiation-exposure risk constitute major concerns for SWL in this specific population [2].

On the other hand, published data, to date, have clearly demonstrated that despite excellent stone-free rates obtained in a single session along with ongoing miniaturization process, PNL has the greatest risk of major complications [3], [4], [5]. For this reason, PNL is generally reserved for stones >20 mm and for the ones when other treatment modalities have failed or would probably fail due to certain reasons [3], [4].

The acceptability and utilisation of the mini, ultramini and the micro PCNLs is on the rise and the complication rate of these procedures is comparable with the RIRS and is significantly low. Nevertheless, the complications such as the risk of bleeding requiring transfusion, pleural and visceral injury, although low, have not been completely eliminated, even with the miniaturized PCNLs[6,7,8,9].

RIRS has become an important treatment option for kidney stones in pediatric patients with the development of new-generation ureteroscopy and holmium laser. It is an effective method in the proximal ureter, collecting duct system, and, especially, lower calyx calculi[10].

Flexible ureteroscopy (FURS) has been applied in recent years to the treatment of urinary stones. FURS presents overt advantages over other techniques,

including improved resolution and increased optical field, high stone-free rate, reduced risk of bleeding, limited surgical injury, good repeatability, and speedy recovery; in addition, further miniaturization is possible[11–13]. In children and infants, who have a relatively high stone recurrence rate, FURS could be performed repeatedly [14].

- Several studies were conducted on RIRS for pediatric renal stones and proved its safety and efficacy. However, RIRS in pediatrics has crossed many milestones, yet many areas need further research, and larger data are required to make RIRS the procedure of choice for renal stone management in children .

OBJECTIVE AND HYPOTHESIS:

- In this study, we will evaluate the feasibility, stone-free rate, and complication rate of RIRS for renal stones in a pediatric population.
- We hypothesize that miniaturized equipment allows experienced urologists to deal with pediatric renal stones safely and effectively .

MATERIALS AND METHODS:

- **STUDY DESIGN:** A Prospective, single-arm interventional study
- **STUDY SETTING:** Urology department/ Al-Hussein and Bab El'Sharia , Al-Azhar University Hospitals
- **STUDY PERIOD:** Two years
- **STUDY POPULATION:**

All children (≤ 18 years), with renal stones ≤ 2 cm indicated for treatment.

Exclusion criteria:

- Active urinary tract infection(UTI)
- Uncorrectable coagulation disorders.
- Concomitant pathology that need intervention in the same setting.
- Stone in a calyceal diverticulum.

- Abnormal renal anatomy
- Urinary tract obstruction distal to the stone.

Informed written consent will be obtained from the patient parents before inclusion in the study.

Parents should be told about the goals of the surgery, likely modifications during surgery, common complications and their treatments, period of hospitalization, postoperative protocol.

• STUDY PROCEDURE:

◊ Preoperative evaluation:

- Medical history and physical examination
- Urinalysis, CBC, and serum creatinine
- Plain X-ray KUB and abdominal ultrasonography
- Abdominal low-dose NCCT
- Contrast imaging (CT or IVU), if detailed calyceal anatomy is needed.
- Routine preoperative laboratory investigations and anesthetic workup.
- Informed consent (Parental consent)

◊ RIRS procedure:

- General anesthesia
- Prophylactic antibiotic
- Preoperative stenting (DJ), near 2 wks before RIRS.
- Without ureteral access sheath
- Under direct visualization and/or fluoroscopy guidance.
- Disposable flexible ureteroscope 8.6 Fr / 7.5 Fr, and Ho. YAG Laser for stone disintegration.
- PO ureteral stenting: external ureteric catheter or DJ stent.

◊ Postoperative evaluation and follow-up:

➤ 1st PO day:

- Monitoring of general condition, vital signs, and urine colour

- *CBC, abdominal USG and plain X-ray KUB*
- *Removal of urethral catheter ± Ureteric catheter, if patient is generally stable with clear urine.*
- *Patient will be discharged home on oral antibiotic and on demand analgesic.*

➤ 2nd PO week and 2nd PO month:

- *History and Ex., urinalysis, s. creatinine, abdominal USG and plain X-ray KUB or NCCT.*
- *The need for another lab or imaging studies or 2 nd RIRS session and time of DJ removal will be decided according to the PO follow-up findings.*
- *DJ will be removed after 2 weeks if (uncomplicated + Stone free).*

▪ STUDY PARAMETERS

- ◊ *Demographic data and preoperative clinical characteristics*
- ◊ *Scope-to-stone access*
- ◊ *Operative time*
- ◊ *Fluoroscopy time*
- ◊ *Postoperative ureteral stenting method*
- ◊ *Intra- and post-operative complications*
- ◊ *Hospitalization time*
- ◊ *Postoperative pain (young children)*
- ◊ *Analgesic dosage*
- ◊ *Unscheduled hospital visits*
- ◊ *Reintervention*
- ◊ *Rehospitalization*

Results:

▪ Data analysis

- ◊ *The 1ry end points are the feasibility of the technique (as evaluated by scope to-stone access rate) and SFR (as evaluated by postoperative imaging studies, 2 months after surgery).*
- ◊ *Patients will be stratified into 3 groups if sufficient (1) Infants and preschool children (upto 6 yrs); (2) Primary school children (>6 – 12 yrs); and Young children (>12 –18 yrs).*
- ◊ *The feasibility and outcomes of RIRS, overall and in each group, will be Analyzed using the SPSS program.*

Data Will be analyzed using Statistical Program for Social Science (SPSS) version 24. Qualitative data were expressed as frequency and percentage. Quantitative data were expressed as mean \pm SD. **Mean (average):** the central value of a discrete set of numbers, specifically the sum of values divided by the number of values. **Standard deviation (SD):** is the measure of dispersion of a set of values. A low SD indicates that the values tend to be close to the mean of the set, while a high SD indicate that the values are spread out over a wider range.

The following tests will be done:

- **A one-way analysis of variance (ANOVA):** when comparing more than two groups.
- **Chi-square test:** will be used when comparing categorized data.
- **Probability (P-value)**
 - P-value < 0.05 was considered significant.
 - P-value < 0.001 was considered as highly significant.
 - P-value > 0.05 was considered insignificant.

DISCUSSION:

SUMMERY & CONCLUSION:

ARABIC SUMMARY:

References:

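### The three ordered age bands are compared only with tests that ignore their order, and no estimate with an interval is planned for how outcomes change with age; one pre-specified age analysis should be added beside them

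*Combined protocol and SAP*

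**What the plan says.** The Data analysis section (under Results) states that "Patients will be stratified into 3 groups if sufficient (1) Infants and preschool children (upto 6 yrs); (2) Primary school children" will be formed, together with a third band running from above 12 to 18 years. The bands are consecutive cuts of one variable, age. The section adds: "The feasibility and outcomes of RIRS, overall and in each group, will be Analyzed using the SPSS program".

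The list of tests that follows has two entries: one-way ANOVA, "when comparing more than two groups", and the chi-square test, which "will be used when comparing categorized data". The decision rule is "P-value < 0.05 was considered significant", with larger values labelled insignificant. Categorical data are summarised as frequencies and percentages, and quantitative data as mean and SD. No trend test, linear contrast, regression, analysis of age in years or confidence interval is named.

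The study is single-arm, so the age bands are the only comparison groups defined. The primary endpoints are overall quantities: "The 1ry end points are the feasibility of the technique (as evaluated by scope to-stone access rate) and SFR".

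**The concern.** ANOVA and chi-square on three groups each spend 2 degrees of freedom on any difference among the bands. They return the same P-value if the bands are shuffled, and they treat an infant and a six-year-old alike. If outcomes change steadily with age, a 1-df analysis that uses the order, or age in years, is more likely to show it.

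Reporting is also at stake. Percentages and means by band will be available, but nothing says how precisely a relation with age is estimated. With a significant/insignificant label as the only inferential output, a gradient that the tests miss could be read as evidence that the procedure works equally well at all ages.

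**Working it through.** **Inputs from the document.** Three bands cut at 6 and 12 years, ANOVA and chi-square, alpha 0.05. Sidedness is not stated; two-sided is assumed.

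**Not in the document.** Sample size, band sizes, expected rates, SDs and any age effect. There is no planned figure to reproduce, and every size and rate below is an assumption.

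**Step 1: where the loss comes from.** With band sizes n_i, successes k_i, pooled rate p and scores s = 0, 1, 2:

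- chi-square (2 df): X² = Σ (k_i − n_i p)² / [n_i p(1 − p)], critical value 5.99
- linear trend (1 df): Z² = [Σ k_i (s_i − s̄)]² / [p(1 − p) Σ n_i (s_i − s̄)²], critical value 3.84

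Put expected counts in, with 20 per band:

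- Linear pattern 65/80/95% (p = 0.80). X²: 20 × (0.15² + 0 + 0.15²) / 0.16 = 5.63. Z²: (20 × 0.30)² / (0.16 × 40) = 36 / 6.4 = 5.63. The signal is the same and the trend test has the lower hurdle.
- Step pattern: contrast (−1, 0, 1) against shape (−2, 1, 1) keeps 3² / (2 × 6) = 0.75 of the signal, which roughly cancels the lower hurdle.
- Only the middle band differs: contrast (−1, 0, 1) against (1, −2, 1) keeps 0.

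**Step 2: sample-size equivalent for a linear gradient.** For 80% power, 1 df needs non-centrality (1.960 + 0.842)² = 7.85, and 2 df needs 9.63. The ratio is 9.63 / 7.85 = 1.23, or about 23% more patients. At 7.85 the 2-df test has 70.9% power. If age is uniform, three equal bands keep 8/9 of its variance, so against age in years the ratio is 1.23 × 9/8 = 1.38.

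**Step 3: simulated power, binary outcome.**

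| Stone-free rate by band | Band sizes | Chi-square | Trend |
|---|---|---|---|
| 65/80/95% | 20/20/20 | 0.58 | 0.71 |
| 60/75/90% | 20/20/20 | 0.50 | 0.62 |
| 60/75/90% | 30/30/30 | 0.70 | 0.80 |
| 65/80/95% | 12/24/24 | 0.54 | 0.61 |
| 60/75/90% | 12/24/24 | 0.47 | 0.54 |
| 80/85/90% | 20/20/20 | 0.10 | 0.15 |
| 65/90/90% (step) | 20/20/20 | 0.54 | 0.56 |
| 65/90/90% (step) | 30/30/30 | 0.72 | 0.72 |
| 65/90/90% (step) | 12/24/24 | 0.46 | 0.38 |
| 65/95/95% (step) | 12/24/24 | 0.70 | 0.62 |
| 95/80/95% (middle band) | 30/30/30 | 0.45 | 0.005 |

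In the five 30-point linear scenarios the gain is 7 to 13 points.

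**Step 4: simulated power, continuous outcome** (age uniform on 0.5 to 18 years).

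| Pattern | n | ANOVA on bands | Regression on age in years |
|---|---|---|---|
| Linear, correlation 0.30 | 60 | 0.49 | 0.66 |
| Linear, correlation 0.30 | 90 | 0.68 | 0.83 |
| 0.6 SD step at age 6 | 60 | 0.45 | 0.38 |
| 0.6 SD step at age 6 | 90 | 0.63 | 0.54 |

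The gain for a linear relation is 15 to 17 points; the loss for a step is 7 to 9. Repeat runs moved these figures by about 1 to 3 points.

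**Step 5: type I error.** Each test alone is near 0.05. Declaring an age effect if either test is significant gives about 0.06 to 0.08.

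**The case against.** The strongest reply is that the plan never sets out to find a gradient. Its objective is "we will evaluate the feasibility, stone-free rate, and complication rate of RIRS for renal stones in a pediatric population", its hypothesis concerns miniaturized equipment, and the bands are formed only if numbers allow. For an unordered question about any difference between bands, ANOVA and chi-square are valid and hold their error rate. All of this stands. A reader might infer that the bands exist to look for an age gradient and that the tests therefore fail their purpose; the document gives no reason for the bands, so that inference is unsupported.

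A reader might also infer that a drop in performance confined to the youngest children would more often be missed. The step rows show otherwise: the planned tests are level with the trend test when bands are equal and ahead of it when the youngest band is small. Nothing in the document says whether an age effect would be a gradient or a threshold.

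Nor is it right that the plan yields only P-values, since rates and means by band are planned. What is absent is a slope or odds ratio for age and an interval around it.

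Finally, under a mild gradient (80/85/90%, 20 per band) either test usually misses the effect, so changing the test rescues little there. That too stands. An interval would at least show that such data are inconclusive.

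**Conclusion.** The point holds as a modest improvement to a secondary, conditional analysis. The bands are ordered, the listed tests ignore that order and the ages within each band, and no estimate with an interval is planned for how outcomes change with age. For a roughly linear effect the cost is about 7 to 13 points of power against a trend test and about 15 to 17 against regression on age in years, in the 30-point and correlation-0.30 scenarios above. The size cannot be fixed more closely without the missing sample size, band sizes and rates.

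The figures do not justify replacing the planned tests. They do as well or better for a step at the youngest band and far better for a non-monotone pattern. The overall access rate and stone-free rate are not affected. The case for an interval does not depend on the shape of the effect, and an analysis on age in years needs no minimum number per band, so it remains available if the bands are not formed.

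**What to change.** Keep the three bands, their descriptive tables, and the planned ANOVA and chi-square. Add one pre-specified age analysis per outcome:

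- Access, stone-free rate and complications: logistic regression on age in years, reported as an odds ratio per year with 95% CI. A linear-by-linear trend test on the bands is an alternative for the P-value, but does not itself give an odds ratio.
- Operative, fluoroscopy and hospitalization time: linear regression on age in years, reported as a slope with 95% CI.

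State in advance whether the age-in-years result or the band comparison is the main age analysis, with the other as a check on shape. Add that P > 0.05 will not be read as equal performance across ages.

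The cost is a few sentences, with no new data, and the methods are available in the planned SPSS version. There are two drawbacks. A second test per outcome adds slight multiplicity (0.06 to 0.08 if either is allowed to count), which naming the main analysis addresses. The trend analysis is less sensitive to step or U-shaped effects, which is why the band comparison must stay.

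### The tests available for the age-group comparisons cannot separate age from stone size, so a size-driven difference in operative time, and less so in SFR, could be read as an age effect

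*Combined protocol and SAP*

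**What the plan says.** The design is "A Prospective, single-arm interventional study" (Materials and Methods, Study design). The Objective section asks about feasibility, stone-free rate (SFR) and complications in children as a whole, and neither it nor the hypothesis mentions age.

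Under Results, Data analysis, the primary endpoints are scope-to-stone access and "SFR (as evaluated by postoperative imaging studies, 2 months after surgery"). Patients are split into three age groups (up to 6, over 6 to 12, over 12 to 18 years), on condition that numbers suffice. Then: "The feasibility and outcomes of RIRS, overall and in each group, will be Analyzed using the SPSS program".

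Two tests follow, at P < 0.05: one-way ANOVA, "when comparing more than two groups", and chi-square, which "will be used when comparing categorized data". No regression, covariate or stratification by stone size appears.

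Stone size enters only through eligibility: children "with renal stones ≤ 2 cm indicated for treatment" (Study population). Preoperative evaluation includes "Abdominal low-dose NCCT". The Study parameters list names "Operative time" and fluoroscopy time but not stone size, which could fall only under the general entry for demographic and preoperative characteristics.

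**The concern.** The age groups are the only set of more than two groups in this single-arm plan, so the ANOVA has no other evident use. The link from each test to each outcome by age is an inference, but a short one.

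Age groups are not randomised, so nothing balances stone size across them. The protocol itself treats size as decisive: the Introduction reserves percutaneous surgery generally for stones above 20 mm, and eligibility stops at 2 cm. Below that limit size varies without restriction, and a larger stone can plausibly take longer to fragment and be harder to clear. If older children have larger stones, or the reverse, the planned tests show a difference between age groups and cannot say whether it persists at a given stone size. A reader of the results could then attribute to age what belongs to stone burden.

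**Working it through.** The documents give no sample size, SD, expected SFR or size-by-age data, so there is no stated figure to reproduce. What follows is illustrative.

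**Assumptions (none from the documents):** equal age groups of m children; stone size SD s = 3.5 mm, restricted to 4-20 mm; mean size rising by d mm from one age group to the next, centred on 12 mm; operative time rising by b min per mm, with residual SD 15 min; no age effect at a given size.

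**Operative time, one-way ANOVA.** Adjacent group means differ by b·d minutes. The within-group variance is 15² + (b·s)². The noncentrality is

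λ = m · 2 · (b·d)² / [15² + (b·s)²]

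and the chance of P < 0.05 comes from the noncentral F with 2 and 3m − 3 degrees of freedom. With b = 3 the variance is 225 + 110.25 = 335.25. For m = 20 and d = 2, λ = 20 · 2 · 36 / 335.25 = 4.30. The formula ignores the size limits; the simulation (1,000 runs per cell) clips sizes to them.

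| m | d (mm) | λ | ANOVA, formula | ANOVA, simulated | ANCOVA with size, simulated |
|---|---|---|---|---|---|
| 20 | 0 | 0 | 5% | 4.5% | 5.0% |
| 20 | 1 | 1.07 | 13.4% | 13.5% | 5.2% |
| 20 | 2 | 4.30 | 42.2% | 42.6% | 4.7% |
| 20 | 3 | 9.66 | 77.9% | 75.0% | 5.2% |
| 40 | 0 | 0 | 5% | 5.6% | 5.2% |
| 40 | 1 | 2.15 | 23.4% | 24.2% | 5.1% |
| 40 | 2 | 8.59 | 73.8% | 74.8% | 5.7% |
| 40 | 3 | 19.33 | 98.0% | 97.9% | 4.7% |

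**A more cautious version.** Truncating the size distribution at 4 and 20 mm, instead of clipping it, pulls nominal means of 10/12/14 mm to about 10.3/12.0/13.7 (step about 1.69 mm) and reduces the within-group size variance to about 10.1 mm².

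- b = 3, m = 17 (n = 51): λ = 34 · (3 · 1.69)² / (225 + 9 · 10.1) = about 2.8, giving 28%.
- b = 3, m = 33 (n = 99): λ = about 5.4, giving 52%.
- b = 1.5, m = 17: λ = 34 · (1.5 · 1.69)² / (225 + 2.25 · 10.1) = about 0.88, giving 12%.
- b = 1.5, m = 33: λ = about 1.7, giving 19%.

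ANCOVA gives 4-5% in these cases. Even with no size-age link, including size cuts the residual variance by about 9-29%, so adjustment is useful either way.

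**SFR, chi-square.** With SFR 85% at 12 mm and the odds of being stone free falling by a factor of 1.25 per mm, chi-square gives P < 0.05 for d = 0/1/2/3 mm in 4.1/6.4/12.6/22.0% of runs (m = 20) and 4.9/7.0/19.9/41.5% (m = 40). An ordinary logistic test adjusted for size gives 6.6-9.2% and 5.5-7.1%, somewhat above 5% because failures are few.

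**Can SFR be adjusted at all?** If SFR is 95% at 8 mm and 65% at 18 mm, mean sizes of 10/12/14 mm give about 90/86/81% by age group. Expected failures are 17 · (0.10 + 0.14 + 0.19) = 7.3 at n = 51 and 33 · 0.43 = 14.2 at n = 99. At n = 51, fewer than 10 failures occur in about 82% of trials, so a logistic model would seldom be usable at that size.

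**The case against.** A reader might infer that the planned tests will produce false-positive age effects and that the trial will draw wrong conclusions about feasibility and outcome by age. The documents do not support that, for four reasons.

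- **No age claim is planned.** Objective and hypothesis are silent on age, and the grouping is conditional. Reporting outcomes by group is legitimate description.
- **The percentages above are not type I error rates of the planned tests.** If SFR is 90/86/81% by age group, the groups do differ, and chi-square answers correctly whether they do. The result misleads only if it is taken as an effect of age at a given stone size.
- **The size-age link is assumed.** With no link the unadjusted tests stay near 5% (4.1-5.6%). With 1 mm steps chi-square is only about 4-8%.
- **The primary results stand.** Overall SFR and overall access need no adjustment, and nothing here connects stone size with scope-to-stone access.

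It would also go too far to say that size is already a study variable. That it must be known is inferred from the 2 cm limit and the NCCT.

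All of this stands, and it limits the point to the secondary age comparisons. It does not remove the point: the link cannot be known before data collection, and adding size after seeing a significant age result would be post hoc.

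**Conclusion.** The concern holds in a limited form. As written, the age comparisons cannot distinguish age from stone size. The omission matters most for operative time, where under the cautious assumptions a purely size-driven difference reaches P < 0.05 in 12-28% of trials at n = 51 and 19-52% at n = 99, against 4-5% with ANCOVA. It matters less for SFR, where the effect is smaller and few failures restrict what can be adjusted.

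These figures rest on assumed size steps between age groups, an assumed size SD and assumed effects of size on outcome. The documents supply none of them, and with no size-age link the problem disappears. The change is worth making because it costs little and sharpens the continuous comparisons even then.

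**What to change.** In Study parameters, name the largest stone diameter on preoperative NCCT as a recorded variable, and report its distribution by age group. In Data analysis:

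- Keep the unadjusted age-group results, labelled as description.
- For operative time and fluoroscopy time, and for hospital stay (transformed if skewed), add an SPSS GLM (ANCOVA) with the three planned age groups and stone diameter. Base any statement about an age effect on the adjusted estimate with its 95% CI.
- For SFR, tabulate age group within two size bands (≤10 mm and >10-20 mm) with exact CIs, as description. Fit a penalised logistic model adjusted for diameter only if there are about 10 or more failures; otherwise make no age claim.

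The cost is a few lines of SAP text and a little analysis time, with no new patients or imaging. Adjustment for size does not remove confounding by other factors such as stone location or number, and the report should say so.

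### Classical one-way ANOVA across age groups of unfixed size may not hold its 5% level for the secondary continuous parameters if spread also differs by age

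*Combined protocol and SAP*

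**What the plan says.** All from the combined protocol and SAP.

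- **Test.** Results, Data analysis names two tests: one-way analysis of variance, to be used "when comparing more than two groups", and chi-square for categorized data. It mentions no unequal-variance version, variance check, transformation or rank-based alternative.
- **Level.** "P-value < 0.05 was considered significant".
- **Groups.** "Patients will be stratified into 3 groups if sufficient": up to 6 years, over 6 to 12, and over 12 to 18. Results are to be analysed overall and in each group. The design is single-arm, and no other grouping with more than two levels is defined.
- **Who enters.** Study population: "All children (≤ 18 years), with renal stones ≤ 2 cm indicated for treatment". There is no age quota, target sample size or expected number per age group.
- **Outcomes.** "The 1ry end points are the feasibility of the technique (as evaluated by scope to-stone access rate) and SFR". Both are proportions. The Study parameters list adds operative time, fluoroscopy time and hospitalization time, which are the natural candidates for ANOVA.

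**The concern.** The classical F test estimates one common variance from all groups. With equal group sizes, moderate differences in spread do little harm. With unequal sizes the pooled estimate is dominated by the largest group. If the smallest group is the most variable, the denominator is too small and the test rejects too often. If the largest group is the most variable, it rejects too rarely.

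Here the age-group sizes depend on which children present over two years, and it is plausible, though not documented, that procedure times vary more in one age band than another. What is at stake is the meaning of a significant or non-significant label on an age comparison of these times. The issue is unequal variance. Skewness is a separate matter, but it limits how well the remedy works.

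**Working it through.** **Inputs.** From the documents: three groups and a 0.05 level. Assumed, because the documents give neither: the group sizes and the SDs (arbitrary units).

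**Step 1: the stated level.** With equal SDs, normal data and no true difference, simulation of the classical F test rejects in about 5% of trials at every set of sizes tried. The stated 0.05 is therefore reproduced when variances are equal. With 40,000 runs the simulation standard error is √(0.05 × 0.95 / 40,000) ≈ 0.1 percentage point.

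**Step 2: why it moves.** Write n_i and σ_i for the size and SD of group i, N for the total and k = 3. With no true difference in means:

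- E(between-group mean square) = Σ(1 − n_i/N)σ_i² / (k − 1)
- E(within-group mean square) = Σ(n_i − 1)σ_i² / (N − k)

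The ratio should be 1. For sizes 10/20/40 with SDs 30/20/15:

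- between: (60/70 × 900 + 50/70 × 400 + 30/70 × 225) / 2 = 1,153.6 / 2 = 576.8
- within: (9 × 900 + 19 × 400 + 39 × 225) / 67 = 24,475 / 67 = 365.3
- ratio: 1.58, so the test is too liberal

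With the SDs reversed (15/20/30) the figures are 432.1 and 667.5, a ratio of 0.65, so the test is too conservative. At 20/20/20 the ratio is exactly 1 whatever the SDs.

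**Step 3: false-positive rates by simulation** (normal data, equal means, nominal 5%; sizes and SDs in the same group order).

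| Sizes | SDs | Ratio from step 2 | Classical ANOVA |
|---|---|---|---|
| 10/20/40 | 30/20/15 | 1.58 | about 15% |
| 10/20/40 | 15/20/30 | 0.65 | about 1.6% |
| 10/20/30 | 30/20/15 | 1.45 | about 12% to 13% |
| 10/20/30 | 15/20/30 | 0.72 | about 2% |
| 15/20/25 | 30/20/15 | 1.19 | about 9% |
| 15/20/25 | 15/20/30 | 0.85 | about 4% |
| 20/20/20 | 30/20/15 | 1.00 | about 6% |
| 15/20/25 | 22.5/18.75/15 | 1.11 | about 7% |
| 15/20/25 | 15/18.75/22.5 | 0.91 | about 4% |

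Welch's ANOVA stays near 5% in every row.

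**Step 4: sensitivity.** With an SD ratio of only 1.2, ANOVA gives 4.3% to 5.6% at 15/20/25 and 3.7% to 7.3% at 10/20/40. At the other extreme, 10/30/60 with a 3-fold ratio gives 1.1% to 23.8%. A larger sample does not help: with SDs in the ratio 1:1.5:2, in either order, sizes 10/20/30 give 2.5% to 12.0% and 20/40/60 give 2.4% to 12.2%.

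**Step 5: skewed data.** Times are bounded at zero and may be right-skewed.

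- Moderate skew (gamma, shape 2), 10/20/40, equal SDs: ANOVA 5.0%, Welch 6.3%.
- Strong skew (lognormal, shape 0.8), 10/20/40, equal SDs: ANOVA about 4.5%, Welch 7.4%.
- Strong skew, 10/20/40, SDs 18/16.5/15: ANOVA 6.1%, Welch 8.3%.
- Strong skew, 10/20/40, SDs 30/20/15: ANOVA 13.6%, Welch 10.5%.

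So on untransformed, strongly skewed data with unequal groups, Welch is not at 5% either, and it is worse than ANOVA when the SDs are similar.

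**The case against.** The strongest case against is that every driver of the effect is assumed. The plan gives no sizes and no SDs. Unequal sizes, unequal spread and a particular pairing of the two must all occur together, and milder inputs leave the test close to 5%. The comparison is secondary, the age split is made only if numbers suffice, and neither the objective nor the hypothesis concerns age differences in times. The plan also does not rule out Welch's version, and the remedy can do worse than ANOVA on strongly skewed data.

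Most of this stands. It sets the severity at the lowest level, and it means the percentages are illustrations. It does not remove the point. One-way ANOVA named without qualification is ordinarily read as the pooled F test. Nothing in the design makes the groups equal. If the split is made, the plan offers no protection against unequal variance.

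A reader might infer three stronger things, none of which the documents support:

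- That the groups will be unequal with different spread, so that an error rate of up to 15% is to be expected. Unequal sizes are a reasonable inference from the absence of a quota, but they are not stated, and nothing is said about spread by age.
- That the primary results are in doubt. Access rate and stone-free rate are proportions. They fall under chi-square when compared by age, and the overall single-arm estimates involve no ANOVA.
- That switching to Welch costs nothing but a little power. Step 5 shows otherwise for strongly skewed times.

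**Conclusion.** The point holds in a limited form. As written, the plan's only test for continuous outcomes across age groups does not protect its 0.05 level when group sizes and variances both differ. The distortion can go either way. With a 2-fold SD ratio and normal data it ranges from negligible at equal sizes (about 6%) to about 1.6% to 15% at 10/20/40. With a 1.5-fold ratio at 15/20/25 it is about 4% to 7%. These figures rest wholly on assumed sizes, SDs and normality. Only the secondary continuous parameters are touched, and only if the age split is made. This is a worthwhile refinement, not a flaw that threatens the study's conclusions.

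**What to change.** In Data analysis, replace one-way ANOVA for age-group comparisons with Welch's one-way ANOVA, and add Games-Howell for any pairwise statement. Use it unconditionally, not after a preliminary test of variances. For times that are clearly right-skewed, run it on log-transformed values. Name those parameters before looking at results by age.

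Two consequences of the log scale should be written down. The comparison becomes one of geometric means. A rule for zeros is also needed: the procedure allows direct visualization without fluoroscopy, so some fluoroscopy times could be zero.

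**Cost.** One or two lines of text, with no new data and no design change. If variances are in fact equal, the simulated power loss was about 1 percentage point at 20/20/20 and 2 to 3.5 points at 10/20/30 or 10/20/40. If strongly skewed data are left untransformed with unequal groups, Welch's error rate can rise to about 7% to 11% and exceed that of ANOVA when SDs are similar. That is why the log-scale provision belongs with the change.
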